1.0 Objectives

Primary Objectives:

- a) Identify the rate of SLN (sentinel lymph node) positivity for eyelid sebaceous gland carcinomas.
- b) Identify the false negative events associated with SLN biopsy for sebaceous gland carcinomas.

Secondary Objective:

Record any side effects associated with SLN biopsy for sebaceous gland carcinoma of the eyelid.

2.0 Background

Sebaceous gland carcinoma of the eyelid is a rare cancer with a tendency for regional nodal metastasis. Clinically obvious regional nodal metastasis is detected in 10-20% of patients with sebaceous gland carcinoma of the eyelid according to most series.

Sentinel lymph node mapping and selective lymphadenectomy is a technique that has been successful in identifying patients with cutaneous melanoma who have microscopic regional lymph node metastasis. An early therapeutic lymph node dissection is subsequently performed in patients proven to harbor occult metastatic disease. This technique is well characterized for cutaneous melanomas in most locations. Our group has adapted SLN biopsy technique for conjunctival melanoma and eyelid sebaceous gland carcinoma.^{5,8-11,13} The potential survival benefit for patients with nodal metastasis treated with neck dissection followed by radiotherapy or systemic adjuvant therapy provides an important impetus for accurate assessment of nodal status in patients with eyelid sebaceous gland carcinoma.

The primary objective of this study is to identify the rate of SLN positivity in patients with eyelid sebaceous gland carcinoma and to determine the false negative events for the same. The SLN positivity rate refers to the number of patients who had a positive SLN on biopsy divided by the total number of patients. The false negative events refer to recurrence in a lymphatic basin that was previously deemed to harbor a "negative" SLN within the first 3 years of follow-up.

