6.0 Evaluation During Study

An ophthalmologic exam to check for recurrence of the eyelid tumor is undertaken every three months (+/- 6 weeks) during the first year and every 6 months (+/- 6 weeks) during years 2-5. A CXR will be performed 1 year (+/- 6 weeks) after removal of the primary tumor. A head and neck CT or MRI or a SPECT /CT scan is done once every 6 months (+/- 6 weeks) during the first year and then once a year (+/- 6 weeks), thereafter and as needed. An ultrasound of regional nodes will be repeated 1 year (+/- 6 weeks) after removal of primary tumor.

A study participant's inability to comply with study policies and procedures, including the inability to comply with recommended follow up visits and testing, will be withdrawn from the study by the study PI.

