9.0 Statistical Considerations

The rate of SLN positivity and the false negative events will be reported using descriptive statistics. Given the rare nature of this cancer, a total patient number of 20 is likely the maximum number that we can feasibly accrue in a few years. The estimated rate of positivity for SLN is about 15% and the estimated rate of false negative events is 8%. Based on these assumptions, the widths of 95% binomial confidence intervals based on 20 patients would be: 5%: 0.25; 10%: 0.30; 15%: 0.35; 20%: 0.38.

10. Data Analysis

Data analysis will be done at the end of patient accrual and follow up.

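### Does the 3-year limit on false negative events lose nodal recurrences found at a late year-3 scan, and should events linked to an eyelid recurrence be split off?

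*Combined protocol and SAP*

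**What the plan says.** Counting false negative events is primary objective (b) in section 1.0. The only definition is in section 2.0: "recurrence in a lymphatic basin that was previously deemed to harbor a" negative "SLN within the first 3 years of follow-up". No start date is given, no rule for dating an event, and no condition on the state of the eyelid.

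Section 6.0 sets the surveillance. Head and neck imaging is six-monthly "during the first year and then once a year (+/- 6 weeks), thereafter and as needed". Regional ultrasound has a single scheduled repeat: "An ultrasound of regional nodes will be repeated 1 year" after the primary is removed. The clinic visit is described as "An ophthalmologic exam to check for recurrence of the eyelid tumor", three-monthly in year 1 and six-monthly in years 2 to 5.

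Section 9.0 plans descriptive statistics for 20 patients. It states that "the estimated rate of false negative events is 8" per cent, and gives 95% interval widths of 0.25, 0.30, 0.35 and 0.38 at observed rates of 5%, 10%, 15% and 20%. Neither section 9.0 nor section 10 adds a rule on event timing.

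**The concern.** Two features of the definition look troublesome.

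**Timing.** A recurrence first seen at a compliant year-3 scan done a few weeks late is outside the limit by calendar date and inside it by nominal visit, so two analysts could classify the same patient differently. The year-3 scan is also the only scheduled nodal imaging near the limit. On the calendar reading the loss would lower the count and so make the biopsy look more reliable than it is. With fewer than two events expected, moving one is visible: 1/20 = 5.0 points, or 1/17 = 5.9 points if 17 patients are node-negative.

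**Pooling.** A nodal recurrence after, or together with, an eyelid recurrence counts the same as an isolated one. It might represent new spread and not a node missed at biopsy, in which case the count mixes two things.

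**Working it through.** **The plan's own figures.** Exact (Clopper-Pearson) 95% intervals for 1, 2, 3 and 4 events in 20 have widths 0.2475, 0.3046, 0.3469 and 0.3793. These round to the stated 0.25, 0.30, 0.35 and 0.38. The precision statement is therefore correct, and nothing below alters it.

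**Dates.** Assume scans and follow-up share a start date, which the protocol does not say. Three years is 3 × 365.25 = 1,095.75 days. A compliant year-3 scan falls within 42 days either side: day 1,053.75 to 1,137.75, or 34.6 to 37.4 months. If it is late, the last routine scan inside the limit is the year-2 scan, at 22.6 to 25.4 months. That leaves 36 − 25.4 = 10.6 to 36 − 22.6 = 13.4 months without routine imaging.

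**Share of events lost on the calendar reading.** If only scans detect recurrence, the events at risk are those arising after the year-2 scan, and about half of year-3 scans are late. So loss ≈ 1/2 × (share of onsets in year 3). The protocol gives no onset distribution, so a range is assumed:

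- Uniform over 3 years: 1/2 × 1/3 = 16.7%
- Exponential with mean m years, truncated at 3: 1/2 × (e^(−2/m) − e^(−3/m)) / (1 − e^(−3/m)), which gives 7.4% (m = 1.5), 4.5% (m = 1.0) and 0.8% (m = 0.5)

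A simulation of 2 million recurrences per case, with every scan varying uniformly within its 6-week window, compares detection by 3.0 years with detection by the end of the year-3 window. The last column also lets each clinic visit find half of the recurrences present, again an assumption.

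| Onset | Scans only | Scans plus visits |
|---|---|---|
| Uniform | 16.8% | 9.8% |
| Exponential, mean 1.5 years | 7.4% | 4.0% |
| Exponential, mean 1.0 year | 4.5% | 2.4% |
| Exponential, mean 0.5 year | 0.8% | 0.4% |

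On the nominal-visit reading every entry is zero.

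**Expected events.** At 8%, 20 × 0.08 = 1.6. With 15% node-positive, 20 × 0.85 = 17 patients are node-negative and 17 × 0.08 = 1.36.

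- Largest loss: 1.6 × 0.168 = 0.27 events, and 0.27/20 = 1.35 points.
- Smallest non-zero loss: 1.36 × 0.004 = 0.005 events.

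**Chance that at least one event is lost**, 1 − (1 − 0.08 × loss)^n:

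- Loss 16.8%, n = 20: 0.24
- Loss 9.8%: 0.15 (n = 20) or 0.125 (n = 17)
- Loss 0.4%, n = 17: 0.005

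**If one event is reclassified.** 1/20 has an exact 95% interval of 0.1% to 24.9%; 2/20 has 1.2% to 31.7%. Each interval contains the other's point estimate.

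**Pooling.** No arithmetic applies. The definition in section 2.0 is unconditional, so there is no doubt about what is counted. Pooling can only raise the count relative to isolated recurrences, so it does not flatter the procedure. The eyelid examinations in section 6.0 already supply what is needed to describe each event.

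**The case for a change.** The strongest case for a change is that this is a primary endpoint with very few events, that the wording admits two readings, and that a clarifying sentence would cost almost nothing. The document is at Version 17, so some outcomes may be known, and a rule written down now would prevent a convenient choice later. All of that is fair. The ambiguity stands, and so does the possibility of a one-event difference.

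It falls short for four reasons. First, a calendar limit at 3 years is a legitimate definition in its own right, and the visit reading is natural in a protocol that allows 6 weeks around each visit; neither produces a wrong analysis. Second, the upper figures of 17% and 24% need the calendar reading, uniform onset and no detection outside scheduled scans all at once, although section 6.0 also provides clinic visits and imaging as needed. Third, a late-detected event is still observed, because examinations run through year 5 and scans continue yearly; only its label is in question. Fourth, the obvious remedy is not free of trouble. A limit set at the year-3 scan could be read as closing the window early when that scan is done up to 6 weeks ahead of time. It would then exclude a recurrence found between the scan and 3 years that the present definition counts. Extending the limit would admit some recurrences that arise after 3 years.

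On pooling, a reader may reasonably want to know whether the eyelid recurred first. But the idea that such nodes were not missed at biopsy has no support in the documents, and dividing about 1.5 expected events into two groups estimates nothing.

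**Conclusion.** No change follows. The missing start date and visit-window rule are gaps that an analyst can fill sensibly when writing up: state the date used, and report each nodal event with its timing and with whether the eyelid tumor had recurred. With one or two events expected, that makes either reading visible to the reader.

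The effect is nil on the visit reading. On the calendar reading it runs from 0.005 to 0.27 expected events, at most 1.35 percentage points at n = 20. The plan has no hypothesis test or decision rule for this effect to alter. These figures rest on a shared start date for scans and follow-up, on dating events by first detection, on the assumed onset distributions and 50% visit detection, and on the plan's 8% rate. The figure of 17 node-negative patients is derived from the plan's 15% positivity. The pooling of events with and without eyelid recurrence is a clear definition and a matter of presentation only.

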3.0 Patient Eligibility

Inclusion Criteria:

- a) Participant must be 18 years of age or over.
- b) Possible or Suspicious sebaceous gland carcinoma of the eyelid.

- c) A CXR (chest x-ray), liver enzymes, and a head and neck CT,a (SPECT/CT) or magnetic resonance imaging (MRI) , and an ultrasound negative for clinical evidence of metastasis.
- d) Patient provided written informed consent. In the event that non-English speaking participants are eligible for this study, a short form (if applicable) or an ICD in their language, will be utilized and completed in accordance with the MDACC Policy for Consenting Non-English Speaking Participants.

Exclusion Criteria:

- a) Pregnant or nursing females.

4.0 Pretreatment Evaluation

Patients who meet the inclusion criteria are evaluated in the Ophthalmology Clinic with a complete ophthalmologic examination. The tumor size, location and extent are characterized. The pathology slides are reviewed by the pathology department at M.D. Anderson and the diagnosis of eyelid sebaceous gland carcinoma is confirmed. A CXR, a CT or MRI of head and neck or a SPECT /CT scan and an ultrasound of regional nodes are obtained to establish lack of clinically identifiable metastatic disease. The patient's ability to undergo surgery under general anesthesia will also be evaluated/assessed at this time. The eligible patients then undergo preoperative lymphoscintigraphy.

NOTE: A serum/blood pregnancy test (i.e., 10cc's) will be obtained, within 7 days prior to SLN mapping and biopsy, for all female patients of child-bearing potential, unless previously ordered as part of standard of care prior to surgery. A negative pregnancy test will be verified on all female patients of child-bearing potential prior to any SLN mapping and biopsy. If beta hcg is outside normal range, a 2nd test will be obtained. If beta hcg is out of range a second time, a gynecologic consult will be obtained.

Women of child-bearing potential (WOCBP) include any female who has experienced menarche and who has not undergone successful surgical sterilization (hysterectomy, bilateral tubal ligation or bilateral oophorectomy) or is not postmenopausal [defined as amenorrhea 12 consecutive months; or women on hormone replacement therapy (HRT) with documented serum follicle stimulating hormone (FSH) level 35mIU/mL]. Even women who are using oral, implanted or injectable contraceptive hormones or mechanical products such as an intrauterine device or barrier methods (diaphragm, condoms, spermicides) to prevent pregnancy or practicing abstinence or where partner is sterile (e.g., vasectomy), should be considered to be of child bearing potential.

5.0 Methodology and Treatment Plan

Within 24 hours prior to planned surgery, patients will be injected with 0.3-0.4 mci of Tc99m-sulfur colloid in 0.15-0.2 cc volume intradermally in 2-4 spots around the eyelid sebaceous gland carcinoma. Multiple standard of care images of the head and neck including SPECT/CT will be obtained in the Nuclear Medicine Department following standard of care

protocols at MD Anderson Cancer Center.. At this point transmission images of the head and neck region will be performed.

Intra-operative Mapping and Sentinel Node Biopsy

On the day of surgery, 0.15-0.2 cc (0.3-0.4 mCi) of Tc99m-Sulfur colloid will be injected intradermally around the primary lesion approximately one hour prior to the procedure, only if it has been more than 24 hours since the prior injection of Tc99m-sulfur colloid.

Intraoperative lymphatic mapping and SLN identification are performed based on the localization of the radioactive colloid in regional lymph nodes. The hand-held gamma probe is used to localize the SLN transcutaneously before a small skin incision is made over the corresponding nodal basin(s), and identification of a SLN is attempted. An SLN is defined as one that collects radiolabeled colloid (at least twice background) within a regional nodal basin. The maximal ex-vivo counts per second are recorded for each SLN. The SLN harvest is considered to be complete when radiotracer uptake in the draining nodal basin(s) is less than twice background. All patients will undergo wide local excision of the eyelid sebaceous gland carcinoma if needed during the same anesthesia session.

The intradermal injection of Tc99m-Sulfur colloid as well as resection of the eyelid tumor will be done by the PI. The intraoperative localization of SLN will be performed by a surgeon from Surgical Oncology or from Head & Neck Surgery.

Excised SLNs are analyzed following the same methodology as in other anatomic locations. Briefly, the SLNs are breadloafed at 2 mm interval. Formalin-fixed, paraffin-embedded and serially sections at 4- μ m intervals are obtained. Initially, one hematoxilin and eosin (H&E) stained slide is examined by routine microscopy. If a metastasis is identified, the diagnosis is rendered. In the report, the size (two dimensions) of the largest metastatic focus, the localization of metastasis (subscapular, intraparenchymal or both) and the presence or absence of the extracapsular extension will be included. If metastasis is not identified in the initial H&E section, a serial level will be obtained and another H&E-stained slide will be examined, along with an immunohistochemical study performed on paraffin-embedded sections. The immunohistochemical study will include a pan-keratin cocktail (containing antibodies against high and low molecular-weight keratins), as well as antisera against epithelial membrane antigen (EMA). The combination of immunohistochemical studies is performed in order to expand the sensitivity of sebaceous carcinoma metastases detection method in SLNs.

6.0 Evaluation During Study

An ophthalmologic exam to check for recurrence of the eyelid tumor is undertaken every three months (+/- 6 weeks) during the first year and every 6 months (+/- 6 weeks) during years 2-5. A CXR will be performed 1 year (+/- 6 weeks) after removal of the primary tumor. A head and neck CT or MRI or a SPECT /CT scan is done once every 6 months (+/- 6 weeks) during the first year and then once a year (+/- 6 weeks), thereafter and as needed. An ultrasound of regional nodes will be repeated 1 year (+/- 6 weeks) after removal of primary tumor.

A study participant's inability to comply with study policies and procedures, including the inability to comply with recommended follow up visits and testing, will be withdrawn from the study by the study PI.

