7.0 Evaluation of Side Effects

There are no significant ocular toxicity expected from SLN biopsy in the periocular region.⁸⁻¹¹ One potential side effect of the SLN biopsy for periocular tumors is the likelihood of involvement of the preauricular (parotid) lymph nodes and the risk of damage to the facial nerve during the dissection and biopsy. In our experience so far, in over 40 patients, there have been no cases of permanent facial nerve paralysis, although 3 patients with ocular tumors have had mild, temporary marginal mandibular nerve paresis, which resolved spontaneously after three weeks. This risk will be discussed with each patient prior to sentinel node biopsy. If facial nerve weakness occurs, the patient will be promptly evaluated by the ophthalmologist for protection of the corneal surface and consideration will be given to periocular reconstructive surgery, if the paresis or palsy is not improved after several months of observation.

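### Does the plan need to say how, when and in whom side effects of sentinel node biopsy are recorded?

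*Combined protocol and SAP*

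**What the plan says.** Section 1.0 lists one secondary objective: "Record any side effects associated with SLN biopsy for sebaceous gland carcinoma of the eyelid".

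Section 6.0 sets the follow-up: "An ophthalmologic exam to check for recurrence of the eyelid tumor is undertaken every three months (+/- 6 weeks) during the first year", then six-monthly exams in years 2 to 5, with imaging alongside. It names no side-effect check. It also covers non-compliance, stating that "the inability to comply with recommended follow up visits and testing, will be withdrawn from the study by the study PI".

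Section 7.0 is the section on side effects. It reports experience in more than 40 patients with no permanent facial paralysis and three cases of "mild, temporary marginal mandibular nerve paresis, which resolved spontaneously after three weeks". It then makes two commitments: "This risk will be discussed with each patient prior to sentinel node biopsy", and "If facial nerve weakness occurs, the patient will be promptly evaluated by the ophthalmologist for protection of the corneal surface". Reconstructive surgery is considered "if the paresis or palsy is not improved after several months of observation".

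Section 9.0 plans descriptive statistics for node positivity and false negative events, and does not mention side effects. Section 10 places the analysis after accrual and follow-up are complete.

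**The concern.** A stated objective would normally come with a data source, an observation window and a denominator, and this one has none of the three. The protocol does say what is recorded where it chooses to: in Section 5.0, "The maximal ex-vivo counts per second are recorded for each SLN".

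Three gaps stand out.

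- **Early.** The routine exam looks for tumour recurrence and probably comes too late to see a short-lived paresis.
- **Late.** Section 7.0 foresees a palsy lasting months, but no section says how long a side effect is followed as study data.
- **Denominator.** Patients can be withdrawn by the PI after surgery, and nothing says whether their side effects stay in the count.

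At stake is the meaning of a result such as 0/20. A reader could not tell whether it came from active questioning, chart review or spontaneous report, nor compare it fairly with the group's earlier experience.

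**Working it through.** **1. The plan's own figure.** Section 9.0 gives 95% interval widths of 0.25, 0.30, 0.35 and 0.38 for rates of 5%, 10%, 15% and 20% in 20 patients. The exact (Clopper-Pearson) interval runs from the 0.025 quantile of Beta(x, n−x+1) to the 0.975 quantile of Beta(x+1, n−x). With n = 20 and x = 1, 2, 3, 4 the widths are 0.2475, 0.3046, 0.3469 and 0.3793, so the plan's figures reproduce to rounding. The same widths apply to a side-effect count of 1 to 4 in 20.

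**2. Timing of the first exam.** No starting point is stated for the exams. If it is surgery, the earliest first visit is 12 or 13 weeks less the 6-week window: 12 − 6 = 6 or 13 − 6 = 7 weeks. The earlier pareses cleared at three weeks, so this visit would not see a similar one. In Section 6.0 the chest x-ray and ultrasound are timed from removal of the primary tumour, and Section 5.0 makes excision at the node procedure conditional on need. If removal came first and exams were timed from it, the first exam could fall sooner after the biopsy. The timing gap therefore depends on an unstated anchor.

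**3. Routes that do not depend on the scheduled exam.** Every patient is told of the nerve risk before biopsy, and facial weakness triggers a prompt ophthalmologist evaluation. The earlier cases were mild and temporary, yet both their occurrence and their time to resolution are known. Such events can evidently come to light.

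**4. How often an event might occur.** Taking more than 40 as 40 (an assumption), 3/40 = 7.5%, exact 95% CI 1.6% to 20.4%.

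| Assumed rate | Expected in 20 (20p) | Chance of at least one, 1 − (1 − p)^20 |
|---|---|---|
| 1.57% | 0.31 | 27% |
| 7.5% | 1.5 | 79% |
| 20.39% | 4.08 | 99% |

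These figures describe occurrence, not failure to record. Nothing in the documents gives a rate of missed events. The three cases were in patients with ocular tumours, not stated to be eyelid sebaceous carcinoma, so carrying the rate over is uncertain.

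**5. What one event or a different denominator does.** 0/20 is 0% (0 to 16.8%). 1/20 is 5.0% (0.1% to 24.9%). If only 16 patients had the procedure (an illustrative assumption), 1/16 is 6.25% (0.2% to 30.2%). The change of denominator moves the estimate by 6.25 − 5.0 = 1.25 percentage points, against an interval about 25 points wide.

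**6. Whether the denominator is really open.** Entry is allowed on a suspected diagnosis, but Section 4.0 has pathology confirm it during the pretreatment evaluation, and eligible patients then go on to lymphoscintigraphy. Section 5.0 describes node identification as attempted, but that attempt follows the skin incision, so those patients were exposed to surgery. The natural population is everyone who had the node surgery. The withdrawal sentence does not say that data already recorded are dropped.

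**The case for a change.** The strongest case for a change is that Section 7.0 does not do what its heading suggests. Its evaluation starts only once someone has noticed facial weakness, it describes care and not data collection, and it covers the facial nerve alone, whereas the objective covers any side effect. Two or three sentences would supply a source, a period and a denominator, with no added visit. In a sample where a single event moves the result from 0% to 5.0%, those details matter to a reader.

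The omission stands: no section provided states these things, and a note on clarity would be fair. The step from there to a needed change does not stand. The objective is to record side effects, whereas the first primary objective is to identify a rate, so a list of events meets it without any proportion. The observation window is in substance given by exams through year 5 and analysis at the end of follow-up, so a lasting palsy would meet repeated visits. The added sentences would also leave the one concrete gap, the early weeks, where it is. Asking at the first exam about an event already over relies on recall, and abstracting post-operative notes assumes records that the documents do not mention.

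**Conclusion.** No change is needed. The plan leaves a detail unwritten that analysts would fill sensibly: list each side effect found by any route up to the end of follow-up, among all patients who had the node surgery, including any later withdrawn. Following the plan as written is not shown to give a wrong or worse side-effect result.

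The effect is small and cannot be measured from the documents. It concerns how a descriptive secondary result in 20 patients is labelled, and both primary objectives are unaffected. With 20 patients the interval around one event is about 25 percentage points wide, which outweighs any plausible choice of denominator.

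The conclusion rests on two readings: that events noticed under Section 7.0 are entered as study data, and that withdrawal ends follow-up without erasing what was already recorded. Neither is stated outright, but nothing in the text contradicts them.
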